#### **10.3.5. Post-Void Residual (PVR) Bladder Ultrasound**

A post-void residual (PVR) bladder ultrasound to assess urinary retention will be performed at Visits 1, 2, 5, 8, 11 and 14 during the first, second, third, and fourth year of the open-label extension study.

#### **10.3.6. AUA Symptom Index**

An AUA Symptom Index, a 7-item Likert-scored scale describing urinary bladder function, will be completed by the Investigator at Visits 1, 2, 5, 8, 11 and 14 during the first, second, third and fourth year of the open-label extension study, to assess the patient's urinary voiding function. The AUA Symptom Index is included in Appendix D of this protocol.

### **10.4. Quality of Life Assessments**

The QOLIE-31-P (Version 2.0) will be utilized to assess quality of life. The QOLIE-31-P assessment must be completed by the patients. Patients who are cognitively impaired and cannot complete the QOLIE-31-P assessment may still participate in the study, by obtaining a waiver for QOLIE-31-P completion from the study medical monitor.

### **10.5. Baseline**

Except for final study eligibility, informed consent and dispensation of open-label extension study medication, the Baseline assessments for the open-label extension study correspond to the assessments performed at the last visit of the Maintenance phase (Visit 9) of Study VRX-RET-E22-302 (See Study Flow Diagram - Appendix A). After completion of all study procedures on the last visit of the Transition phase (Visit 11) of Study VRX-RET-E22-302, patients will be allowed to enter this open-label extension study (VRX-RET-E22-304). All ongoing AEs and concomitant medications at the last visit of the Transition Phase (Visit 11) of Study VRX-RET-E22-302 will need to be transferred and captured on the appropriate open-label extension AE and Concomitant Medication CRF pages. The final study eligibility and informed consent for the open-label extension study should be performed at the last visit of the Transition phase (Visit 11) of Study VRX-RET-E22-302. A urine pregnancy test will be performed on female patients of child-bearing potential, to immediately confirm the non-pregnancy eligibility requirements to enter the VRX-RET-E22-304 study. After confirmation of all final study eligibility requirements and obtaining proper informed consent, open-label study medication (sufficient supply of bottles at appropriate dose strengths = 50 mg, 100 mg, 300 mg) will be dispensed to patients, along with seizure diaries for completion until the next study visit (Visit 1 / Month 1).

### **10.6. Study Visit 1 (Month 1)**

Patients will return for Study Visit 1 (Month 1). At this visit, the following evaluations will be performed:

- Seizure Diary (collection / review of current diary and dispensation of new diary)
- Brief Neurological Exam
- Vital Signs (BP, HR, and Temperature) and Body Weight
- Clinical Laboratory Tests (Blood Chemistries, Hematology, Urinalysis including microscopy)
- 12-lead ECG
- AUA Symptom Index
- PVR Bladder Ultrasound
- Adverse Events
- Concomitant Medication
- Open-Label Study Medication (collect returned medication and dispense new medication)

### **10.7. Study Visit 1a (Month 2)**

Patients will return for Study Visit 1a (Month 2). At this visit, clinical laboratory tests, consisting of the following hematological evaluations (including a differential) will be performed:

- Hemoglobin
- Hematocrit
- RBC Count
- WBC Count
- Platelet count.

### **10.8. Study Visit 2 (Month 3)**

Patients will return for Study Visit 2 (Month 3). At this visit, the following evaluations will be performed:

- Seizure Diary (collection / review of current diary and dispensation of new diary)
- Brief Neurological Exam

- Vital Signs (BP, HR, and Temperature) and Body Weight
- Clinical Laboratory Tests (Blood Chemistries, Hematology, Urinalysis including microscopy)
- 12-lead ECG
- AUA Symptom Index
- PVR Bladder Ultrasound
- Adverse Events
- Concomitant Medication
- QOLIE-31-P Questionnaire (completed by patient)
- Open-Label Study Medication (collect returned medication and dispense new medication)

#### **10.9. Study Visit 2a (Month 4)**

Patients will return for Study Visit 2a (Month 4). At this visit, clinical laboratory tests, consisting of the following hematological evaluations (including a differential) will be performed:

- Hemoglobin
- Hematocrit
- RBC Count
- WBC Count
- Platelet count.

#### **10.10. Study Visit 3 (Month 6)**

Patients will return for Study Visit 3 (Month 6). At this visit, the following evaluations will be performed:

- Seizure Diary (collection / review of current diary and dispensation of new diary)
- Brief Neurological Exam
- Vital Signs (BP, HR, and Temperature) and Body Weight
- Clinical Laboratory Tests (Blood Chemistries, Hematology, Urinalysis including microscopy)
- 12-lead ECG

- Adverse Events
- Concomitant Medication
- QOLIE-31-P Questionnaire (completed by patient)
- Open-Label Study Medication (collect returned medication and dispense new medication)

#### **10.11. Study Visit 3a (Month 8)**

Patients will return for Study Visit 3a (Month 8). At this visit, clinical laboratory tests, consisting of the following hematological evaluations (including a differential) will be performed:

- Hemoglobin
- Hematocrit
- RBC Count
- WBC Count
- Platelet count.

#### **10.12. Study Visit 4 (Month 9)**

Patients will return for Study Visit 4 (Month 9). At this visit, the following evaluations will be performed:

- Seizure Diary (collection / review of current diary and dispensation of new diary)
- Brief Neurological Exam
- Vital Signs (BP, HR, and Temperature) and Body Weight
- Clinical Laboratory Tests (Blood Chemistries, Hematology, Urinalysis including microscopy)
- 12-lead ECG
- Adverse Events
- Concomitant Medication
- QOLIE-31-P Questionnaire (completed by patient)
- Open-Label Study Medication (collect returned medication and dispense new medication)

**10.13. Study Visit 4a (Month 10)**

Patients will return for Study Visit 4a (Month 10). At this visit, clinical laboratory tests, consisting of the following hematological evaluations (including a differential), will be performed:

- Hemoglobin
- Hematocrit
- RBC Count
- WBC Count
- Platelet count.

**10.14. Study Visit 5 (Month 12)**

Patients will return for Study Visit 5 (Month 12). At this visit, the following evaluations will be performed:

- Seizure Diary (collection / review of current diary and dispensation of new diary)
- Complete Physical and Neurological Exam
- Vital Signs (BP, HR, and Temperature) and Body Weight
- Clinical Laboratory Tests (Blood Chemistries, Hematology, Urinalysis including microscopy)
- Serum Pregnancy Test
- 12-lead ECG
- AUA Symptom Index
- PVR Bladder Ultrasound
- Adverse Events
- Concomitant Medication
- QOLIE-31-P Questionnaire (completed by patient)
- Open-Label Study Medication (collect returned medication and dispense new medication)

**10.15. Study Visits after the First Year**

After the first year of open-label extension study, the study visits will occur every 4 months (3 visits per year), and will continue until retigabine is approved and

commercially available, or until the program is discontinued. The assessments for the first 2 study visits of each year will be identical, and the assessments for the last study visit of each year will be identical. To provide guidance, the following study visits and assessments will be performed during the second and third years of the open-label extension study:

**10.15.1. Visit 6 (Month 16)**

Patients will return for Study Visit 6 (Month 16), 4 months after Visit 5. At this visit, the following evaluations will be performed:

- Seizure Diary (collection / review of current diary and dispensation of new diary)
- Brief Neurological Exam
- Vital Signs (BP, HR, and Temperature) and Body Weight
- Clinical Laboratory Tests (Blood Chemistries, Hematology, Urinalysis including microscopy)
- Adverse Events
- Concomitant Medication
- Open-Label Study Medication (Collect returned medication and dispense new medication)

**10.15.2. Visit 7 (Month 20)**

Patients will return for Study Visit 7 (Month 20). At this visit, the following evaluations will be performed:

- Seizure Diary (collection / review of current diary and dispensation of new diary)
- Brief Neurological Exam
- Vital Signs (BP, HR, and Temperature) and Body Weight
- Clinical Laboratory Tests (Blood Chemistries, Hematology, Urinalysis including microscopy)
- Adverse Events
- Concomitant Medication
- Open-Label Study Medication (Collect returned medication and dispense new medication)

**10.15.3. Visit 8 (Month 24)**

Patients will return for Study Visit 8 (Month 24). At this visit, the following evaluations will be performed:

- Seizure Diary (collection / review of current diary and dispensation of new diary)
- Complete Physical and Neurological Exam
- Vital Signs (BP, HR, and Temperature) and Body Weight
- AUA Symptom Index
- PVR Bladder Ultrasound
- Clinical Laboratory Tests (Blood Chemistries, Hematology, Urinalysis including microscopy)
- Serum Pregnancy Test
- 12-lead ECG
- Adverse Events
- Concomitant Medication
- QOLIE-31-P Questionnaire (completed by patient)
- Open-Label Study Medication (collect returned medication and dispense new medication)

**10.15.4. Visit 9 (Month 28)**

Patients will return for Study Visit 9 (Month 28). At this visit, the following evaluations will be performed:

- Seizure Diary (collection / review of current diary and dispensation of new diary)
- Brief Neurological Exam
- Vital Signs (BP, HR, and Temperature) and Body Weight
- Clinical Laboratory Tests (Blood Chemistries, Hematology, Urinalysis including microscopy)
- Adverse Events
- Concomitant Medication
- Open-Label Study Medication (Collect returned medication and dispense new medication)

**10.15.5. Visit 10 (Month 32)**

Patients will return for Study Visit 10 (Month 32). At this visit, the following evaluations will be performed:

- Seizure Diary (collection / review of current diary and dispensation of new diary)
- Brief Neurological Exam
- Vital Signs (BP, HR, and Temperature) and Body Weight
- Clinical Laboratory Tests (Blood Chemistries, Hematology, Urinalysis including microscopy)
- Adverse Events
- Concomitant Medication
- Open-Label Study Medication (Collect returned medication and dispense new medication)

**10.15.6. Visit 11 (Month 36)**

Patients will return for Study Visit 11 (Month 36). At this visit, the following evaluations will be performed:

- Seizure Diary (collection / review of current diary and dispensation of new diary)
- Complete Physical and Neurological Exam
- Vital Signs (BP, HR, and Temperature) and Body Weight
- AUA Symptom Index
- PVR Bladder Ultrasound
- Clinical Laboratory Tests (Blood Chemistries, Hematology, Urinalysis including microscopy)
- Serum Pregnancy Test
- 12-lead ECG
- Adverse Events
- Concomitant Medication
- QOLIE-31-P Questionnaire (completed by patient)
- Open-Label Study Medication (collect returned medication and dispense new medication)

**10.15.7. Visit 12 (Month 40)**

Patients will return for Study Visit 12 (Month 40). At this visit, the following evaluations will be performed:

- Seizure Diary (collection / review of current diary and dispensation of new diary)
- Brief Neurological Exam
- Vital Signs (BP, HR, and Temperature) and Body Weight
- Clinical Laboratory Tests (Blood Chemistries, Hematology, Urinalysis including microscopy)
- Adverse Events
- Concomitant Medication
- Open-Label Study Medication (Collect returned medication and dispense new medication)

**10.15.8. Visit 13 (Month 44)**

Patients will return for Study Visit 13 (Month 44). At this visit, the following evaluations will be performed:

- Seizure Diary (collection / review of current diary and dispensation of new diary)
- Brief Neurological Exam
- Vital Signs (BP, HR, and Temperature) and Body Weight
- Clinical Laboratory Tests (Blood Chemistries, Hematology, Urinalysis including microscopy)
- Adverse Events
- Concomitant Medication
- Open-Label Study Medication (Collect returned medication and dispense new medication)

**10.15.9. Visit 14 (Month 48)**

Patients will return for Study Visit 14 (Month 48). At this visit, the following evaluations will be performed:

- Seizure Diary (collection / review of current diary and dispensation of new diary)
- Complete Physical and Neurological Exam
- Vital Signs (BP, HR, and Temperature) and Body Weight

- AUA Symptom Index
- PVR Bladder Ultrasound
- Clinical Laboratory Tests (Blood Chemistries, Hematology, Urinalysis including microscopy)
- Serum Pregnancy Test
- 12-lead ECG
- Adverse Events
- Concomitant Medication
- QOLIE-31-P Questionnaire (completed by patient)
- Open-Label Study Medication (collect returned medication and dispense new medication)

#### **10.16. Tapering Period**

All patients who discontinue early from study treatment during the open-label extension study will have their study medication tapered over a 3-week period, reducing their daily dose by one-third per week, and return immediately for a final visit. The patients will be instructed to take the tablets from their existing study medication bottles and to follow this tapering procedure:

- During the first week of tapering, patients will no longer take the afternoon dose.
- During the second week of tapering, patients will no longer take the morning and the afternoon doses.
- During the third week of tapering, patients will take no study medication (but will continue their existing background AEDs).

During the first year, these patients should then return for a final visit to complete all assessments and evaluations scheduled for Study Visit 5. During the second year, these patients should then return for a final visit to complete all assessments and evaluations scheduled for Study Visit 8. During the third year, these patients should then return for a final visit to complete all assessments and evaluations scheduled for Study Visit 11. During the fourth year, these patients should then return for a final visit to complete all assessments and evaluations scheduled for Study Visit 14 (Refer to Study Flow Chart in Appendix A).

During the tapering period, a new background AED should not be added until after the patient's final visit unless clinically necessary for patient safety. Unused current study medication bottles will be collected to ascertain compliance. Current study seizure

diaries will be collected and reviewed. Concomitant medications and AED usage will be documented, and adverse events will be recorded.

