#### **9.7. Study Medication**

Study medication will be supplied by Valeant Pharmaceuticals, North America, as film-coated tablets containing 50 mg, 100 mg, or 300 mg of retigabine per tablet. Tablets will be packaged in induction sealed bottles. A sufficient supply of study medication will be provided to each site for completion of the trial, based on the number of patients enrolled, study visit schedule, and the daily doses of patients. Specific dosage instructions will be provided separately to the patient. All study medication will be dispensed by the pharmacy or an appropriately qualified member of the study staff assigned by the Principal Investigator to this task.

Patients will take the established background AEDs from their own prescriptions, and their use will be recorded.

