#### 9.7.1. Dosage Schedule and Mode of Administration

Patients who completed the Transition phase of Study VRX-RET-E22-302 will start with 300 mg three times a day (300 mg TID). Patients who were not able to tolerate the final dose adjustment (750 mg/day) during the last week of the Transition phase of Study VRX-RET-E22-302 will start with 200 mg three times a day (200 mg TID).

If, in the opinion of the Investigator, the patient was not receiving the maximum effective dose, the dose could be increased in weekly intervals of 150 mg/day, up to a maximum of 1200 mg daily (i.e. 400 mg TID). If adverse events considered to be secondary to retigabine occur, the total daily dose could be reduced by 150 mg/day every week, at Investigator discretion, as long as the dose is within 600-1200 mg/day.

At the investigator's discretion, patients may also start with another dose regimen that can be either BID or TID, and is not required to be equally distributed throughout the day (e.g., if a patient experiences somnolence and the investigator decides to dose the patient higher in the evening) as long as the total daily dose is within 600 -1200 mg/day.

After the patient has entered open-label treatment, the Investigator may add new AEDs, as long as these are approved AEDs. In addition, the existing background AED therapy can be adjusted to achieve the best efficacy/safety ratio, as needed, per Investigator discretion. If necessary, in the Investigator's judgment, all background AEDs can be discontinued to achieve monotherapy with retigabine.

Patients who permanently discontinue open-label treatment will have their dose tapered by one-third every week.

Patients will be instructed on the administration procedures for study drug. Study medication will be administered orally with or without food. The 3 daily doses are to be administered with approximately an 8-hour interval between them (for example 7am, 3pm, 11pm). Patients will continue to take their established background AEDs from their own prescriptions.

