**10.20.2. Handling of Withdrawals**

If a patient is withdrawn from the study either at the patient's request or at the Investigator's decision or the patient fails to return, every effort should be made to determine the reason. This information will be recorded on the patient's case report form (CRF) and recorded by IVRS.

All patients who withdraw from the study prematurely, regardless of cause, should have their study medication tapered over a 3-week period, reducing their daily dose by one-

third per week, and follow the tapering procedures outlined in Section 9.12 (Tapering Period).

It is important to obtain follow up data for any patient withdrawn because of an AE, abnormal laboratory test, or ECG finding. In any case, every effort must be made to undertake safety follow up procedures.

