### **13. DOSE MODIFICATIONS**

Patients will be treated with 600-1200 mg/day of retigabine as an adjunct therapy to their current antiepileptic medications (AEDs) or vagal nerve stimulation as established in Study VRX-RET-E22-302.

If, in the opinion of the Investigator, the patient was not receiving the maximum effective dose, the dose could be increased in weekly intervals of 150 mg/day, up to a maximum of 1200 mg daily (i.e., 400 mg TID). If adverse events considered to be secondary to retigabine occur, the total daily dose could be reduced by 150 mg/day every week, at Investigator discretion, as long as the dose is within 600-1200 mg/day.

After the patient has entered open-label treatment, the Investigator may add new AEDs, as long as these are approved AEDs. In addition, the existing background AED therapy can be adjusted to achieve the best efficacy/safety ratio, as needed, per Investigator discretion. If necessary, in the Investigator's judgment, all background AEDs can be discontinued to achieve monotherapy with retigabine.

Patients who permanently discontinue open-label treatment will have their dose tapered by one-third every week.

If a patient experiences a serious adverse event that is categorized to be "life-threatening," all study medication must be discontinued immediately.

All dose modifications and reason(s) must be documented in the patient's source documents and the CRF.

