#### 8.7.1. Dosage Schedule and Mode of Administration

Patients who completed the Transition phase of Study VRX-RET-E22-302 will start with 300 mg three times a day (300 mg TID). Patients who were not able to tolerate the final dose adjustment (750 mg/day) during the last week of the Transition phase of Study VRX-RET-E22-302 will start with 200 mg three times a day (200 mg TID).

If, in the opinion of the Investigator, the patient was not receiving the maximum effective dose, the dose could be increased in weekly intervals of 150 mg/day, up to a maximum of

1200 mg daily (i.e. 400 mg TID). If adverse events considered to be secondary to retigabine occur, the total daily dose could be reduced by 150 mg/day every week, at Investigator discretion, as long as the dose is within 600-1200 mg/day.

After the patient has entered open-label treatment, the Investigator may add new AEDs, as long as these are approved AEDs. In addition, the existing background AED therapy can be adjusted to achieve the best efficacy/safety ratio, as needed, per Investigator discretion. If necessary, in the Investigator's judgment, all background AEDs can be discontinued to achieve monotherapy with retigabine.

Patients who permanently discontinue open-label treatment will have their dose tapered by one-third every week.

Patients will be instructed on the administration procedures for study drug. Study medication will be administered orally with or without food. The 3 daily doses are to be administered with approximately an 8-hour interval between them (for example 7am, 3pm, 11pm). Patients will continue to take their established background AEDs from their own prescriptions.

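### The Section 10.16 taper steps give a one-third weekly reduction only for three equal daily doses, not for the BID or evening-heavy regimens that Section 9.7.1 allows

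*Protocol*

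**What the plan says.** Section 10.16 (Amendment 2) sets a three-week taper for all early discontinuers at one-third of the daily dose per week. It says patients will be instructed to "take the tablets from their existing study medication bottles and to follow this tapering procedure". The steps that follow go by time of day:

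- Week 1: "During the first week of tapering, patients will no longer take the afternoon dose".
- Week 2: the morning dose is dropped too, leaving the evening dose.
- Week 3: no study drug.

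Section 9.7.1 sets the default start at 300 mg TID, or 200 mg TID for patients who did not tolerate the last transition step. It also lets the investigator start a patient on "another dose regimen that can be either BID or TID, and is not required to be equally distributed throughout the day", provided the total stays within 600-1200 mg/day. Its own example is "if a patient experiences somnolence and the investigator decides to dose the patient higher in the evening".

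The one-third rule is repeated in Sections 9.7.1, 9.7.5, 10.20, 10.20.2 and 13, but none of them gives steps for a BID or unequal regimen.

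**The concern.** The two instructions cannot both be met for regimens the protocol expressly allows. A morning-and-evening BID patient has no afternoon dose to drop, so the first step removes nothing. If the evening dose is the largest, the final step to zero must exceed a third.

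The history explains it. The original protocol's dosing section described only three daily doses ("The 3 daily doses are to be administered with approximately an 8-hour interval between them"), and its taper section used the same steps, which fitted. Amendment 1 added the flexible regimens and left the steps alone. Amendment 2 reopened 10.16 only to add the fourth-year final visit.

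At stake is the rate at which a patient with epilepsy comes off an antiepileptic. Section 9.7.1 also allows all background AEDs to be stopped, and 10.16 discourages adding a new one before the final visit unless safety requires it. For a patient on retigabine alone, an oversized last step therefore removes the only antiepileptic drug. No taper-period visit is scheduled; the final visit comes after the taper.

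**Working it through.** **Inputs.** The taper steps and the one-third target come from 10.16. The regimens and the 600-1200 mg/day range come from 9.7.1. The protocol fixes no particular BID or unequal split and does not define BID times, so the splits below are assumptions.

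**Formula.** Let m, a and e be the morning, afternoon and evening doses, with D = m + a + e. Under the 10.16 steps the daily dose runs

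D → m + e → e → 0.

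The weekly reductions, as shares of the starting dose, are a/D, m/D and e/D. All three equal 1/3 only if m = a = e. One-third is read as a third of the pre-taper dose, because the taper reaches zero in week 3.

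**The plan's own figure.** For 300/300/300 the daily dose runs 900 → 600 → 300 → 0, reductions of 300/900 = 33.3% each week. The same holds for equal TID at 600, 750, 1050 and 1200 mg/day. A search of all 50 mg splits at these five totals found only the equal ones giving thirds.

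**Other regimens at 900 mg/day.**

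| Morning/afternoon/evening (mg) | Daily dose, start and weeks 1-3 (mg) | Weekly reduction (% of start) | Last non-zero step (mg) |
|---|---|---|---|
| 300/300/300 | 900, 600, 300, 0 | 33/33/33 | 300 |
| 450/0/450 | 900, 900, 450, 0 | 0/50/50 | 450 |
| 300/0/600 | 900, 900, 600, 0 | 0/33/67 | 600 |
| 200/200/500 | 900, 700, 500, 0 | 22/22/56 | 500 |
| 250/250/400 | 900, 650, 400, 0 | 28/28/44 | 400 |
| 0/450/450 | 900, 450, 450, 0 | 50/0/50 | 450 |
| 450/450/0 | 900, 450, 0, 0 | 50/50/0 | 450, off drug a week early |

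**Across the dose range.** For equal morning-and-evening BID the last step is D/2, against D/3 under the stated rule:

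- At 600 mg/day: 300 mg instead of 200 mg.
- At 1200 mg/day: 600 mg instead of 400 mg.
- The ratio is (D/2)/(D/3) = 1.5 at every dose.

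**What does not depend on the splits.** With two daily doses, one of a, m and e is zero, so one step removes nothing. With any evening share above one-third, e/D exceeds 1/3, so the last step is too large.

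**The case against.** The strongest reply is that the one-third rule governs and does not depend on regimen. It appears in 9.7.1 itself, shortly after the BID option is granted, and in several other sections. On that reading the 10.16 steps are only its TID implementation. An investigator who chose BID would see that there is no afternoon dose to drop, and Sections 9.7 and 17 say specific dosage instructions go to the patient separately.

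Harm is also not demonstrated:

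- Under morning-and-evening BID or evening-heavy TID, the patient reaches zero when planned and takes more drug in weeks 1 and 2, not less: 900/450 or 700/500 mg, against 600/300 mg.
- Nothing in the documents shows that a 50% last step is unsafe, and Section 7.2 reports no withdrawal liability in preclinical testing.
- Existing background AEDs continue, a new one may be added if safety requires it, and unscheduled visits are allowed.

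Much of this stands as a limit on weight. Sites may well correct the steps. The afternoon-based BID splits are less likely than morning and evening, and the early stop arises only from the morning-and-afternoon split. But repeating the one-third rule does not rescue the steps, because that rule is what they contradict, and nothing says which prevails. The separate dosage instructions are not in the documents, and 10.16 has patients instructed to follow the listed steps.

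**Conclusion.** The concern holds. The 10.16 steps meet the protocol's own taper rate only for equal TID dosing and miss it for every other regimen that 9.7.1 permits. On the assumed splits, equal morning-and-evening BID makes the last step 1.5 times the stated size after a week with no reduction; 200/200/500 mg makes it 500/300, about 1.7 times. These sizes rest on the splits, but the direction does not.

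The 300 mg TID and 200 mg TID starts are unaffected, and the number of patients on other regimens is not given. The point should be corrected on patient-safety grounds. It changes no statistical result. Confidence is high in the inconsistency; how often it reaches a patient cannot be judged from the documents.

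**What to change.** In 10.16, keep the dose-dropping steps for equal TID. For any other regimen, define the taper by total daily dose: two-thirds in week 1, one-third in week 2, none in week 3, rounded to available tablet strengths, with the investigator recording how each reduced total is split over the day. The supply is "film-coated tablets containing 50 mg, 100 mg, or 300 mg of retigabine per tablet", and totals reached in 150 mg steps need no rounding, since each result is a multiple of 50 mg:

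| Starting dose (mg/day) | Week 1 | Week 2 | Week 3 |
|---|---|---|---|
| 600 | 400 | 200 | 0 |
| 750 | 500 | 250 | 0 |
| 900 | 600 | 300 | 0 |
| 1050 | 700 | 350 | 0 |
| 1200 | 800 | 400 | 0 |

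Two minor corrections can go in the same amendment, though the point does not rest on them. Section 10.20.2 refers to Section 9.12 for the taper, which is the original protocol's number; it should read 10.16. Sections 10.16 and 10.20.2 should also except life-threatening SAEs, for which Section 13 says "all study medication must be discontinued immediately".

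The cost is a wording amendment with sponsor approval and IRB/IEC/REB review under Section 22, across a multinational study. It adds no scheduled visits or data. Because patients taper from existing bottles, some may need 50 or 100 mg tablets dispensed for the taper. Packages are assigned through the IVRS at scheduled visits, which are four months apart after the first year, so that may occasionally mean an extra dispensing contact.
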